An interim analysis of outcomes out to 30 days on the first 230 subjects was presented at the 2021 Society for Interventional Radiology Annual Conference in March, 2021, with the abstract from this conference published in the Journal of Vascular and Interventional Radiology, as well as earlier conferences.⁵⁸⁻⁶⁰ These subjects (60.7 ± 13.9 years, 52.2% male) were enrolled across 17 sites, with 93.0% having intermediate-risk PE and 7.0% high-risk PE. The average baseline RV/LV ratio was 1.6 ± 0.5 and sPESI was 1.6 ± 1.1 . 96.3% of subjects had elevated biomarkers, and 69.7% of subjects had concomitant DVT. The primary endpoint of composite MAEs occurred in three (1.3%) subjects, all of which were non-ICH major bleeds, and no deaths occurred within 48 hours.

In-hospital outcomes demonstrated significant improvements across several acute parameters. Subjects experienced significant on-table hemodynamic improvements, including a 21.9% decrease in mean pulmonary artery pressure (32.0 mmHg to 25.0 mmHg, $P < 0.0001$) and a 20.1% decrease in heart rate (pre-procedural high of 113.2 bpm to 90.5 bpm immediately post-procedure, $P < 0.0001$). There was only one (0.4%) access site complication. The median post-procedure hospital length of stay was 3.0 [2.0 – 5.1] days and ICU length of stay was 0.0 [0.0 – 1.1] days.

30-day follow up data was available for 201 subjects in this analysis. In this population, there was one death (0.5% mortality), which was unrelated to the device, and there were ten hospital readmissions, one of which was related to the procedure. The average RV/LV ratio improved by 33.2% at a median follow up of 30 days ($P < 0.0001$) and subjects with confirmed baseline dyspnea had a significant improvement from baseline to 30 days (Modified Medical Research Council Dyspnea Scale, 3.0 ± 1.0 to 1.4 ± 1.3 , $P < 0.0001$).

These results of the FLASH all-comer registry demonstrate both safety and efficacy of the FlowTriever System, with a low all-cause mortality rate (0.0% at 48 hours, 0.5% at 30 days; no device-related deaths), along with significant and immediate hemodynamic improvements and continued improvements in RV/LV ratio and dyspnea out to 30 days.

FLAME Study Design and Status

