For subjects getting discharged from or transferred off the ICU and returning again during the index hospitalization, up to a maximum of 7 days after the Index Procedure, the total hours of all ICU admissions or transfers during that period (i.e., after the Index Procedure and until hospital discharge up to a maximum of 7 days) are used for assessing ICU LOS.

Subjects who had been in the ICU leading up to the Index Procedure, but *not* returning to the ICU after the end of the Index Procedure, are *not* considered to have had an ICU Admission per the endpoint definition.

For the win ratio primary endpoint, ICU admission and ICU LOS are characterized hierarchically as follows:

1. No ICU Admission
2. ICU Admission, lasting between 0 – 24 hours
3. ICU Admission, lasting longer than 24 hours

SECONDARY ENDPOINTS

The secondary endpoints of the study will assess safety, effectiveness, and utility measures, as follows:

- Composite clinical endpoint constructed as a win ratio hierarchy of the following four components, assessed at hospital discharge or at 7 days after the index procedure, whichever is sooner:
 - All-cause mortality, or
 - Intracranial hemorrhage (ICH), or
 - Major bleeding per ISTH definition⁴, or
 - Clinical deterioration defined by hemodynamic or respiratory worsening, and/or escalation to a bailout therapy
- Individual components of the win ratio composite endpoint, assessed at hospital discharge or at 7 days after the index procedure, whichever is sooner:
 - All-cause mortality
 - Intracranial hemorrhage (ICH)

- Major bleeding per ISTH⁴ definition
- Clinical deterioration defined by hemodynamic or respiratory worsening, and/or escalation to a bailout therapy
- ICU admission and ICU length of stay during the index hospitalization and following the index procedure
- All-cause mortality within 30 days from index procedure
- PE-related and all-cause readmission within 30 days from index procedure
- Device and drug-related serious adverse events through the 30 day visit
- Clinically Relevant Non-Major (CRNM) and Minor bleeding events through hospital discharge or at 7 days after the index procedure, whichever is sooner
- Change in right-ventricular/left-ventricular (RV/LV) ratio from baseline to 24 hour visit, as measured by echocardiography or CT
- mMRC Dyspnea score at 24 hour visit and 30 day visit
- Length of total hospital stay and post-index-procedure hospital stay (to a maximum of 30 days)

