5.4.7. ICU admission and ICU length of stay

ICU admission and ICU length of stay, post index procedure and following the index procedure, will be analyzed as with the following null and alternative hypotheses:

$H_0: p_{IF1} \leq p_{IC1}$ and $p_{IF2} \geq p_{IC2}$ and $p_{IF3} \geq p_{IC3}$ versus $H_A: p_{IF1} > p_{IC1}$ or $p_{IF2} < p_{IC2}$ or $p_{IF3} < p_{IC3}$

where p_{IF1} represents the proportion of subjects without ICU admission in the FlowTriever System group, p_{IF2} represents the proportion of subjects with 0-24 hours ICU stay in the FlowTriever System group, p_{IF3} represents the proportion of subjects with > 24 hours ICU stay in the FlowTriever System group, p_{IC1} represents the proportion of subjects without ICU admission in the CDT group, p_{IC2} represents the proportion of subjects with 0-24 hours ICU stay in the CDT group, p_{IC3} represents the proportion of subjects with > 24 hours ICU stay in the CDT group. The hypothesis will be tested using a Fisher's exact test.

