5.4.12. Change in RV/LV Ratio

Change in right-ventricular/left-ventricular (RV/LV) ratio from baseline to 24 hour visit, as measured by echocardiography or CT, will be analyzed as with the following null and alternative hypotheses:

$$H_0: \mu_{RF} \leq \mu_{RC} \text{ versus } H_A: \mu_{RF} > \mu_{RC}$$

where μ_{RF} represents the mean reduction in the RV/LV ratio treated from baseline to 24 hour visit in the FlowTriever System group, and μ_{RC} represents the mean reduction in the RV/LV ratio treated from baseline to 24 hour visit in the CDT group. The hypothesis will be tested using a Wilcoxon Rank Sum test.

5.4.13. mMRC Dyspnea Score at 24 Hour Visit

The mMRC Dyspnea score at 24 hour visit will be analyzed as with the following null and alternative hypotheses:

$$H_0: p_{mD24hF0} \leq p_{mD24hC0} \text{ and } p_{mD24hF1} \geq p_{mD24hC1} \text{ and } p_{mD24hF2} \geq p_{mD24hC2} \text{ and } p_{mD24hF3} \geq p_{mD24hC3} \text{ and } p_{mD24hF4} \geq p_{mD24hC4}$$

versus

$$H_A: p_{mD24hF0} > p_{mD24hC0} \text{ or } p_{mD24hF1} < p_{mD24hC1} \text{ or } p_{mD24hF2} < p_{mD24hC2} \text{ or } p_{mD24hF3} < p_{mD24hC3} \text{ or } p_{mD24hF4} < p_{mD24hC4}$$

PROPRIETARY AND CONFIDENTIAL

	PEERLESS Study: Statistical Analysis Plan	Version 5.0 March 22, 2024 Page 22 of 25
---	--	--

where $p_{mD24hFz}$ represents the proportion of subjects with mMRC Dyspnea Score equal to z at 24 hour visit in the FlowTriever System group, where $z = 0, 1, 2, 3$, and 4 ; and, $p_{mD24hCz}$ represents the proportion of subjects with mMRC Dyspnea Score equal to z at 24 hour visit in the CDT group, where $z = 0, 1, 2, 3$, and 4 . The hypothesis will be tested using a Fisher's exact test.

5.4.14. mMRC Dyspnea Score at 30 Day Visit

The mMRC Dyspnea score at 30 day visit will be analyzed as with the following null and alternative hypotheses:

$H_0: p_{mD30dF0} \leq p_{mD30dC0}$ and $p_{mD30dF1} \geq p_{mD30dC1}$ and $p_{mD30dF2} \geq p_{mD30dC2}$ and $p_{mD30dF3} \geq p_{mD30dC3}$ and $p_{mD30dF4} \geq p_{mD30dC4}$

versus

$H_A: p_{mD30dF0} > p_{mD30dC0}$ or $p_{mD30dF1} < p_{mD30dC1}$ or $p_{mD30dF2} < p_{mD30dC2}$ or $p_{mD30dF3} < p_{mD30dC3}$ or $p_{mD30dF4} < p_{mD30dC4}$

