where $p_{mD30dFz}$ represents the proportion of subjects with mMRC Dyspnea Score equal to z at 30 day visit in the FlowTriever System group, where $z = 0, 1, 2, 3$, and 4 ; and, $p_{mD30dCz}$ represents the proportion of subjects with mMRC Dyspnea Score equal to z at 30 day visit in the CDT group, where $z = 0, 1, 2, 3$, and 4 . The hypothesis will be tested using a Fisher's exact test.

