5.6. Controlling for Multiplicity

For the primary and secondary endpoints related to safety, α is set to 0.05, to conservatively include all potential safety signals. The secondary endpoints listed below are considered as safety endpoints:

- Composite clinical endpoint constructed as a win ratio hierarchy of the following four components, assessed at hospital discharge or at 7 days after the index procedure, whichever is sooner:
 - All-cause mortality, or
 - Intracranial hemorrhage (ICH), or
 - Major bleeding per ISTH³ definition, or
 - Clinical deterioration defined by hemodynamic or respiratory worsening, and/or escalation to a bailout therapy
- Four Individual components of the win ratio composite endpoint, assessed at hospital discharge or at 7 days after the index procedure, whichever is sooner:
 - All-cause mortality
 - Intracranial hemorrhage (ICH)
 - Major bleeding per ISTH³ definition

PROPRIETARY AND CONFIDENTIAL

The information contained in this document is the sole property of Inari Medical

	PEERLESS Study: Statistical Analysis Plan	Version 5.0 March 22, 2024 Page 24 of 25
---	--	--

- Clinical deterioration defined by hemodynamic or respiratory worsening, and/or escalation to a bailout therapy
- All-cause mortality within 30 days from index procedure
- PE-related and all-cause readmission within 30 days from index procedure
- Device and drug-related serious adverse events through the 30 day visit
- Clinically Relevant Non-Major (CRNM) and Minor bleeding events through hospital discharge or at 7 days after the index procedure, whichever is sooner

For the secondary endpoints not related to safety, the family-wide type I error rate will be controlled at one-sided $\alpha=0.025$ using the Bonferroni correction with an effective number of independent tests. The typical Bonferroni correction assumes all tests are independent and is therefore extremely conservative. An alternative approach to estimate the effective number of independent tests for the correlated tests has been proposed by Gao et al (2008)⁹. Therefore, the α to adjust for multiplicity is simply

$$\frac{\text{familywide type I error}}{\text{effective number of independent tests}}$$

The secondary endpoints listed below are considered as non-safety endpoints:

- ICU admission and ICU length of stay post index procedure and following the index procedure
- Change in right-ventricular/left-ventricular (RV/LV) ratio from baseline to 24 hour visit, as measured by echocardiography or CT

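### The superiority alternatives for ICU stay and mMRC are met when FlowTriever patients shift from a middle level to a worse one, and the Fisher test named for them has no layout or direction rule

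*SAP*

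**What the plan says.** SAP 5.4.7 splits ICU use into no admission, 0-24 h and more than 24 h, and gives the alternative as "H_A: p_{IF1} > p_{IC1}$ or $p_{IF2} < p_{IC2}$ or $p_{IF3} < p_{IC3". Any one clause is enough.

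SAP 5.4.13 and 5.4.14 do the same for mMRC at 24 hours and 30 days: more FlowTriever patients at score 0, or fewer at any one of scores 1 to 4. The score-1 clauses are "p_{mD24hF1} < p_{mD24hC1" and "p_{mD30dF1} < p_{mD30dC1".

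For all three endpoints the analysis is a single sentence: "The hypothesis will be tested using a Fisher's exact test". None of the sections says whether the table is 2x3 or 2x5 or a set of 2x2 tables, or how the direction of a significant result is judged.

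SAP 5.6 places these endpoints in a directional family: "For the secondary endpoints not related to safety, the family-wide type I error rate will be controlled at one-sided" 0.025, divided by an effective number of independent tests.

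The levels are ordered. Protocol section 5 introduces them with "For the win ratio primary endpoint, ICU admission and ICU LOS are characterized hierarchically as follows", running from no admission to more than 24 hours. For mMRC, a higher score means worse dyspnea.

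**The concern.** An alternative that supports a superiority claim should hold only when FlowTriever is better. This one also holds when the share in a middle level falls because patients moved to a worse level.

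The named test does not repair this. Read as one omnibus test, Fisher's test ignores the order of the levels and has no tail to match a one-sided 0.025. Read as one-sided 2x2 tests, one per clause, it follows the printed alternative but counts a shrinking middle level as a FlowTriever win. The plan does not choose between the readings, and it does not say whether the 5.6 divisor would count category tests. The layout could then be chosen after the data are seen.

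At stake are three of the seven non-safety secondary tests: ICU stay, mMRC at 24 hours and mMRC at 30 days. The other four are RV/LV change, post-procedure hospital stay, PEmb-QoL and EQ-5D-5L.

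**Working it through.** The SAP gives no planning figure for these tests, so there is none to reproduce. The sample size of 432 belongs to the primary endpoint.

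**Step 1: logic, with no assumed rates.** Let d1, d2, d3 be FlowTriever minus CDT in the proportions with no ICU stay, 0-24 h and more than 24 h. They sum to zero, so with all three non-zero there are 2^3 - 2 = 6 sign patterns. H0 requires d1 ≤ 0, d2 ≥ 0 and d3 ≥ 0, so only (-, +, +) lies in it. The pattern (-, -, +), with FlowTriever worse throughout, lies in H_A. For mMRC there are 2^5 - 2 = 30 patterns and only one lies in H0.

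**Step 2: inputs for illustration.**
- 275 per arm: the cap of 550 in SAP 5.1, randomised 1:1.
- FlowTriever arm: set near the FLASH interim results in Protocol section 3. There, "ICU length of stay was 0.0 [0.0 – 1.1] days" as a median; if the brackets are quartiles, at least half had no stay and about a quarter exceeded 24 h (1.1 days = 26.4 h). For dyspnea FLASH reports "Modified Medical Research Council Dyspnea Scale, 3.0 ± 1.0 to 1.4 ± 1.3" from baseline to 30 days, in subjects with confirmed baseline dyspnea.
- CDT arm: assumed, because the documents give no CDT distribution.
- Significance level: between 0.025 and 0.025/7 = 0.0036 if each endpoint counts once. If every category is a test, 0.025/(4+3+5+5) = 0.025/17 = 0.0015.

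**Step 3: ICU, FlowTriever 143/60/72 v CDT 143/95/37.**
- Pairs won by FlowTriever: 143×(95+37) + 60×37 = 21,096.
- Pairs lost: 143×(60+72) + 95×72 = 25,716.
- Ties: 275² - 21,096 - 25,716 = 28,813.
- Win probability: (21,096 + 28,813/2)/75,625 = 0.469.
- Tie-corrected Wilcoxon: (35,502.5 - 37,812.5)/√2,879,453 = -1.36; negative is against FlowTriever.
- Exact 2x3 Fisher (full enumeration): p = 0.000066.
- One-sided 2x2 Fisher, fewer FlowTriever patients at 0-24 h (60 v 95): p = 0.0006.

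**Step 4: mMRC 0-4, FlowTriever 88/78/51/33/25 (mean 1.38, SD 1.29) v CDT 88/110/51/18/8.** The 2x5 Fisher gives p = 0.0008 (Monte Carlo), the score-1 one-sided test p = 0.0026, and Wilcoxon z = -2.18. All four Fisher p-values in steps 3 and 4 pass 0.0036; all but the score-1 value pass 0.0015.

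**Step 5: the omnibus p-value has no direction.** FlowTriever 55/110/110 v CDT 55/165/55 (harm) and the same table with the arms exchanged (benefit) both give p = 3.6×10⁻⁷. The one-sided Wilcoxon p for FlowTriever better is 0.9998 and 0.0002 respectively.

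**Step 6: how often a win is declared on the category-by-category reading**, when ICU patients truly move from 0-24 h to more than 24 h (20,000 simulated trials, FlowTriever 52/22/26%):

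| Assumed CDT % | at 0.025 | at 0.025/3 | at 0.025/7 | one-sided Wilcoxon at 0.025 |
|---|---|---|---|---|
| 52/32/16 (10-point shift) | 72-73% | 57% | 44-45% | 0.1-0.2% |
| 52/28/20 (6-point shift) | 34% | 20% | 12% | 0.5% |

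**Step 7: the omnibus reading inside the written H0.** With harm of pattern (-, +, +), the omnibus test (chi-square as stand-in) at 0.025 rejects in 94% of trials for FlowTriever 8/46/46 v CDT 20/40/40%, and in 63% for 52/22/26 v 64/17/19%. At 0.025/7 the figures are 82% and 37%.

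**The case against.** The strongest reply is that the wording points to one omnibus test. Each section refers to one hypothesis and one test, and 5.6 lists ICU as one endpoint and mMRC as one at each of two visits. On that reading the rates in step 6 do not arise. The omnibus p-value is valid against equal distributions, and the rejections in step 7 detect a real difference; they mislead only if significance is read as superiority. SAP 5.4.17 requires counts and percentages, so a reader can see the direction. This is fair, and the omnibus layout is the more natural one. It still does not deliver the one-sided test that 5.6 calls for, and a confirmatory directional claim should not rest on reading percentages afterwards.

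The CDT arms are also assumed, and for ICU they run against the protocol's expectation: section 1 says thrombolytic infusion typically needs ICU admission. A high rate of wrongly declared wins needs movement from the middle to the worst level with little change in the best. Under a uniform worsening (odds ratio 1/1.5), the category reading declares an ICU win in 1 to 28% of trials at uncorrected 0.025, depending on the assumed distribution, with the low end at 52/22/26. In step 3, z = -1.36 does not itself establish harm. These points limit the forecasts but leave step 1 untouched. The documents give no comparable expectation for mMRC.

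Finally, the SAP's other Fisher and Wilcoxon sections name no tail either. There, though, a one-parameter alternative supplies the side; a test on three or five levels has no such side.

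**Conclusion.** The concern holds. As printed, the alternatives in 5.4.7, 5.4.13 and 5.4.14 include outcomes in which FlowTriever is worse, and the named test has neither the layout nor the direction rule needed for a one-sided 0.025 family. On the category reading a worsening can be declared a win; on the omnibus reading a significant result does not say which arm did better. That conclusion rests on the text alone. The rates in steps 6 and 7 depend on assumed CDT distributions and are illustrations.

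The reach is three secondary tests. The primary Finkelstein-Schoenfeld analysis ranks the ICU levels in order and is unaffected. The change should be made, but it does not threaten the main result.

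**What to change.** In each of the three sections, replace the hypotheses with one ordered statement. H0: the two distributions are equal, or FlowTriever is stochastically worse. H_A: FlowTriever is stochastically better. Order ICU as none, 0-24 h, more than 24 h, and mMRC from 0 (best) to 4. Test with the one-sided Wilcoxon rank-sum test with midranks for ties, and count each endpoint once in the 5.6 divisor. Report the win probability with a 95% CI, for which the bootstrap in SAP 5.3 can be reused, and keep the category counts and percentages.

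Distributions that cross fall under neither hypothesis. If the null is instead a win probability of at most 0.5, use a variance valid under that null, such as Brunner-Munzel. In an extreme case with equal win probabilities (FlowTriever 35/30/35 v CDT 5/90/5%), the rank-sum test rejects 4.4% at a nominal 2.5%, and Brunner-Munzel 2.5%.

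The cost is SAP wording in three sections, with no new data and a test already in the plan. The ordered test can lose power when a benefit is not an ordered shift: for FlowTriever 52/22/26 v CDT 35/35/30% with 250 per arm, the omnibus test has 94% power and the one-sided Wilcoxon 86%. The change must be fixed before unblinded analysis.

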5.4.8. PE-related Readmission within 30 Days from Index Procedure

PE-related readmission within 30 days from index procedure will be analyzed as with the following null and alternative hypotheses:

$H_0: p_{PRF} \geq p_{PRC}$ versus $H_A: p_{PRF} < p_{PRC}$

where p_{PRF} represents the proportion of subjects had PE-related readmission within 30 days in the FlowTriever System group while p_{PRC} represents the proportion of subjects had PE-related readmission within 30 days in the CDT group. The hypothesis will be tested using a Fisher's exact test.

5.4.9. All-cause Readmission within 30 Days from Index Procedure

All-cause readmission within 30 days from index procedure will be analyzed as with the following null and alternative hypotheses:

$H_0: p_{ARF} \geq p_{ARC}$ versus $H_A: p_{ARF} < p_{ARC}$

where p_{ARF} represents the proportion of subjects had all-cause readmission within 30 days in the FlowTriever System group while p_{ARC} represents the proportion of subjects had all-caused readmission within 30 days in the CDT group. The hypothesis will be tested using a Fisher's exact test.

PROPRIETARY AND CONFIDENTIAL

The information contained in this document is the sole property of Inari Medical

5.4.10. Clinically Relevant Non-Major Events at Discharge/at 7 Days after the Index Procedure

Clinically relevant non-major (CRNM) events through hospital discharge or at 7 days after the index procedure, whichever is sooner, will be analyzed as with the following null and alternative hypotheses:

$$H_0: p_{CRF} \geq p_{CRC} \text{ versus } H_A: p_{CRF} < p_{CRC}$$

where p_{CRF} represents the proportion of CRNM events in the FlowTriever System group while p_{CRC} represents the proportion of CRNM events in the CDT group. The hypothesis will be tested using a Fisher's exact test.

5.4.11. Minor Bleeding Events at Discharge/at 7 Days after the Index Procedure

Minor bleeding events through hospital discharge or at 7 days after the index procedure, whichever is sooner, will be analyzed as with the following null and alternative hypotheses:

$$H_0: p_{MBF} \geq p_{MBC} \text{ versus } H_A: p_{MBF} < p_{MBC}$$

where p_{MBF} represents the proportion of minor bleeding events in the FlowTriever System group while p_{MBC} represents the proportion of minor bleeding events in the CDT group. The hypothesis will be tested using a Fisher's exact test.

5.4.12. Change in RV/LV Ratio

Change in right-ventricular/left-ventricular (RV/LV) ratio from baseline to 24 hour visit, as measured by echocardiography or CT, will be analyzed as with the following null and alternative hypotheses:

$$H_0: \mu_{RF} \leq \mu_{RC} \text{ versus } H_A: \mu_{RF} > \mu_{RC}$$

where μ_{RF} represents the mean reduction in the RV/LV ratio treated from baseline to 24 hour visit in the FlowTriever System group, and μ_{RC} represents the mean reduction in the RV/LV ratio treated from baseline to 24 hour visit in the CDT group. The hypothesis will be tested using a Wilcoxon Rank Sum test.

5.4.13. mMRC Dyspnea Score at 24 Hour Visit

The mMRC Dyspnea score at 24 hour visit will be analyzed as with the following null and alternative hypotheses:

$$H_0: p_{mD24hF0} \leq p_{mD24hC0} \text{ and } p_{mD24hF1} \geq p_{mD24hC1} \text{ and } p_{mD24hF2} \geq p_{mD24hC2} \text{ and } p_{mD24hF3} \geq p_{mD24hC3} \text{ and } p_{mD24hF4} \geq p_{mD24hC4}$$

versus

$$H_A: p_{mD24hF0} > p_{mD24hC0} \text{ or } p_{mD24hF1} < p_{mD24hC1} \text{ or } p_{mD24hF2} < p_{mD24hC2} \text{ or } p_{mD24hF3} < p_{mD24hC3} \text{ or } p_{mD24hF4} < p_{mD24hC4}$$

PROPRIETARY AND CONFIDENTIAL

	PEERLESS Study: Statistical Analysis Plan	Version 5.0 March 22, 2024 Page 22 of 25
---	--	--

where $p_{mD24hFz}$ represents the proportion of subjects with mMRC Dyspnea Score equal to z at 24 hour visit in the FlowTriever System group, where $z = 0, 1, 2, 3$, and 4 ; and, $p_{mD24hCz}$ represents the proportion of subjects with mMRC Dyspnea Score equal to z at 24 hour visit in the CDT group, where $z = 0, 1, 2, 3$, and 4 . The hypothesis will be tested using a Fisher's exact test.

5.4.14. mMRC Dyspnea Score at 30 Day Visit

The mMRC Dyspnea score at 30 day visit will be analyzed as with the following null and alternative hypotheses:

$H_0: p_{mD30dF0} \leq p_{mD30dC0}$ and $p_{mD30dF1} \geq p_{mD30dC1}$ and $p_{mD30dF2} \geq p_{mD30dC2}$ and $p_{mD30dF3} \geq p_{mD30dC3}$ and $p_{mD30dF4} \geq p_{mD30dC4}$

versus

$H_A: p_{mD30dF0} > p_{mD30dC0}$ or $p_{mD30dF1} < p_{mD30dC1}$ or $p_{mD30dF2} < p_{mD30dC2}$ or $p_{mD30dF3} < p_{mD30dC3}$ or $p_{mD30dF4} < p_{mD30dC4}$

where $p_{mD30dFz}$ represents the proportion of subjects with mMRC Dyspnea Score equal to z at 30 day visit in the FlowTriever System group, where $z = 0, 1, 2, 3$, and 4 ; and, $p_{mD30dCz}$ represents the proportion of subjects with mMRC Dyspnea Score equal to z at 30 day visit in the CDT group, where $z = 0, 1, 2, 3$, and 4 . The hypothesis will be tested using a Fisher's exact test.

